8.1.3 Supportive and sensitivity analyses of the primary efficacy variable

Different sensitivity analyses to evaluate the effect of missing observations on the primary analysis findings will be done. The first sensitivity analysis will be performed in the same way as the primary analysis but will use PPS instead. A further analysis will utilize the Last Observation Carried Forward (LOCF) approach and the FAS; missing values will be replaced by the last observed post-Baseline value of the variable and the analysis will be performed on the resulting dataset.

8.2 Statistical analysis of the secondary efficacy variables

The secondary efficacy variables are the changes from Baseline in MG-Composite and MGADL scores to Visit 9 (Day 29) prior to the first infusion of IMP in Dosing Period 2.

The MG-composite score comprises 10 items, each of which is weighted differently in the calculation of the overall score. The overall score ranges from 0 to 50, with a higher score indicating more severe disease. The items of MG-composite score will be displayed in a glossary. All individual item results will be listed. The total score will be listed and used to calculate change from baseline and used in descriptive summaries and for efficacy analysis. Total score will be used to determine responder state, which will be flagged in the listing and descriptively summarized.

The complete list of items and scores are provided in [Table 14-2](#).

The MGADL score comprises of 8 items, each with a score of 0 to 3. The items of MGADL will be displayed in a glossary. The total MGADL score ranges from 0 to 24 with a higher score indicating more disability. The complete list of items and scores are provided in [Table 14-3](#). The total score will be calculated according to the rules set down in [Section 14.3](#). All individual item results will be listed. The MGADL listing will contain total score for an interpolated visit at Day 57, where the total score is derived based on interpolation of Day 50 and 64. If total score on either day 50 or day 64 is not available no interpolated score will be derived. The total score after single item imputation will be listed and used to calculate change from baseline and used in descriptive summaries and for efficacy analysis, interpolated data from Day 57 will be part of the descriptive summary. Total score will be used to determine responder state, which will be flagged in the listing and descriptively summarized.

A comparison summary of MGADL showing absolute scores of Visit 9 (day 29), interpolated Day 57 and their differences will be presented by treatment group of second treatment period (Placebo - UCB7665 7mg/kg, Placebo - UCB7665 4mg/kg, UCB7665 7mg/kg - UCB7665 7mg/kg, UCB7665 7mg/kg - UCB7665 4mg/kg).

8.2.1 MG-composite score

The MG-composite score will be analyzed utilizing the MMRM ANCOVA. A 1-sided hypothesis test will be performed to test the hypothesis of superiority of UCB7665 7mg/kg vs placebo at Visit 9. The null hypothesis is that the mean change from Baseline in MG-composite score is larger or equal in the UCB7665 7mg/kg group than the placebo group. The alternative hypothesis is that the mean change from Baseline in MG-composite score is smaller in the UCB7665 7mg/kg group than the placebo group.

The change from baseline of the MG-composite score will be analyzed for the FAS using a MMRM ANCOVA that includes terms for week (as categorical effect), treatment group, the Baseline MG-composite score, and the interaction between treatment group and week. The model will define subject as a random effect and utilize an unstructured covariance pattern. Least Squares (LS) Means for changes from Baseline at Visit 9 (Day 29) for each treatment group will be presented together with LS mean differences (UCB7665 - 7mg/kg vs placebo), p-value and 1 sided 95% CI.

For subjects who prematurely withdraw for any reason before Visit 9 (Day 29), data collected during the PEOT Visit will be used to impute MG-composite scores at the next consecutive

visit.. There will be no sensitivity analysis for the MG-composite score. Subjects without baseline value will not be analyzed.

8.2.2 MG activities of daily living

Since the MGADL does not have repeated observations per subject, the MGADL score will be analyzed via a simplified version of the model. The change from baseline MGADL will be analyzed for the FAS using a ANCOVA that includes terms for treatment group and the Baseline score. Least Squares (LS) Means for changes from Baseline at Visit 9 for each treatment group will be presented together with LS mean differences (UCB7665 - 7mg/kg vs placebo), p-value and 1 sided 95% CI. Subjects without baseline or Visit 9 observations will not be analyzed. There will be no sensitivity analysis for MGADL.

8.3 Analysis of other efficacy variables

8.3.1 Summaries of efficacy variables

Values and change from Baseline in QMG, MG-Composite and MGADL at each scheduled visit will be descriptively summarized at each scheduled assessment during Treatment and Observation Periods. MGFA classification will be summarized during Treatment and Observation Periods.

8.3.2 Muscle weakness severity and fatigability scale

The Muscle weakness severity and fatigability scale is displayed in [Section 14.4](#). It consists of a domain for muscle weakness on a total scale from 0 to 90 and a domain for fatigability on a total scale from 0 to 36. The total scale ranges from 0 to 126 with a higher score indicating more disability. The items of the muscle weakness and fatigability scale will be displayed in a glossary. All individual item results will be listed per time point, including total per domain and total. The total score will be used to calculate change from baseline and used in descriptive summaries and for efficacy analysis. Total score will be descriptively summarized by treatment and time point.

Muscle weakness severity and fatigability scale at each assessed post-Randomization Visit (during Dosing Period 1 including Visit 9) will also be analyzed utilizing the MMRM approach.

A 1-sided hypothesis test will be performed to test the hypothesis of superiority of UCB7665 7mg/kg vs placebo at Visit 9. The null hypothesis is that the mean change from Baseline in muscle weakness score is larger or equal in the UCB7665 7mg/kg group than the placebo group. The alternative hypothesis is that the mean change from Baseline in muscle weakness score is smaller in the UCB7665 7mg/kg group than the placebo group.

The change from baseline of the muscle weakness score will be analyzed for the FAS using a MMRM ANCOVA that includes terms for week (as categorical effect), treatment group, the Baseline muscle weakness score, and the interaction between treatment group and week. The model will define subject as a random effect and utilize an unstructured covariance pattern. Least Squares (LS) Means for changes from Baseline at Visit 9 (Day 29) for each treatment group will be presented together with LS mean differences (UCB7665 - 7mg/kg vs placebo), p-value and 1 sided 95% CI.

For subjects who prematurely withdraw for any reason before Visit 9 (Day 29), data collected during the PEOT Visit will be used to impute muscle weakness scores at the next consecutive visit.

The complete lists of items and scores are provided in [Table 14-4](#) and [Table 14-5](#).

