9.3 Patient-reported outcomes

Subjects will complete 4 patient-reported outcomes (PROs) and participate in 1 subject exit interview as per time points mentioned in the schedule of study assessments in Section 5.2. Study personnel other than the treating physician should administer the PROs. The PROs should be completed by the subject themselves in a quiet place.

The PROs and the subject exit interview should be completed in the following order: MG muscle weakness and fatigability, Fatigue, MGADL and MGII, followed by the subject exit interview (which will be performed only at the FV). The PROs should only be checked for completeness. On dosing days, the PROs will be completed prior to dosing.

MG muscle weakness and fatigability

60⁹.3.1 The MG muscle weakness and fatigability instrument (Appendix 18.3) consists of 27 items across 2 domains: 18 muscle weakness severity items and 9 symptom fatigability items. The subject will be asked to choose the response option that best describes the severity of muscle UCB7665

weakness symptoms over the past 7 days using a 6-point Likert scale ("none" to "very severe") and how frequently they experienced symptom fatigability over the past 7 days using a 5-point Likert scale ("none of the time" to "all of the time"), respectively. The muscle weakness score ranges from 0 to 90; the fatigability score ranges from 0 to 36. The overall score ranges from 0 to 126, with a higher result indicating more severe muscle weakness and fatigability.

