14.3.2 Other efficacy analyses

The secondary variables and change from Baseline in QMG score, MG-Composite score, MGADL score, MGII score, muscle weakness severity and fatigability scale score and fatigue scale score, at each assessed post-Randomization Visit (during Dosing Period 1 including Visit 9) will also be analyzed utilizing the MMRM approach similarly to the change from Baseline in QMG for the FAS as described in Section 14.3.1.

QMG, MG-Composite, and MGADL responder rates at each assessed post-Randomization Visit (during Dosing Period 1) will be compared between the 2 Treatment Groups utilizing Fisher's exact test.

The percentage of subjects with each MGFA classification at each scheduled assessment during Treatment and Observation Periods will be calculated.

Psychometric analyses of the newly developed measures MG muscle weakness severity and fatigability and fatigue scales will be performed blinded from treatment arms. The association between PROs and clinical variables will also be explored, as well as the association between the various PROs. A psychometric analysis of the MG muscle weakness severity and fatigability scale and fatigue scale using Rasch analysis will be performed, but reported separately from the CSR.

Changes in MCD of the IPI, and normal fiber pairs in jitter (SFEMG) will be summarized using descriptive statistics, by treatment group and time point, including changes from Baseline. A reduction in MCD of $\geq 9\mu s$ in jitter (SFEMG) studies will also be summarized using descriptive statistics, by treatment group and time point, including changes from Baseline.

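### SAP 8.3.2 assigns the 0-126 total of the muscle weakness and fatigability scale to efficacy analysis, but writes the hypotheses and model for the muscle weakness score, which the protocol defines as the 0-90 domain

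*SAP*

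**What the plan says.** SAP 8.3.2 describes the instrument in two parts: "It consists of a domain for muscle weakness on a total scale from 0 to 90 and a domain for fatigability on a total scale". The fatigability range is given as 0-36. The section then gives the sum: "The total scale ranges from 0 to 126 with a higher score indicating more disability". The same paragraph assigns that sum to the analysis: "The total score will be used to calculate change from baseline and used in descriptive summaries and for efficacy analysis". The two domain totals are to be listed at each time point. The section gives them no change from baseline and no summary. The sentence that introduces the repeated-measures (MMRM) analysis names the whole scale.

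The specification that follows uses another term. The null hypothesis, with placebo as comparator, reads "The null hypothesis is that the mean change from Baseline in muscle weakness score is larger or equal in the UCB7665 7mg/kg group than the". Next, the model sentence reads "The change from baseline of the muscle weakness score will be analyzed for the FAS using a MMRM ANCOVA". The alternative hypothesis, the baseline covariate and the rule for carrying PEOT data to the next visit use the same term.

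Protocol 9.3.1 gives that term a range: "The muscle weakness score ranges from 0 to 90; the fatigability score ranges from 0 to 36". It calls the 0-126 quantity the overall score. Protocol 14.3.2, which lists the variables to be analysed by MMRM, names "muscle weakness severity and fatigability scale score and fatigue scale score".

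**The concern.** One SAP section designates one score for the test and then specifies the test for another. A programmer who follows the designating sentence fits the 0-126 total. One who follows the model sentence, with the protocol's definition of the term, fits the 0-90 domain. On the second route the 1-sided p-value and confidence limit at Visit 9 would not describe the variable that Protocol 14.3.2 names, and fatigability on this instrument would not be tested at all. The conflict is in the operative sentences, not in background description.

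**Working it through.** **Score ranges.** Inputs from Protocol 9.3.1: 18 weakness items on a 6-point scale and 9 fatigability items on a 5-point scale. Coding from zero is inferred from the stated ranges.

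- Weakness domain: 18 × (6 − 1) = 90
- Fatigability domain: 9 × (5 − 1) = 36
- Total: 90 + 36 = 126

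These reproduce the ranges in both documents, so 0-90 and 0-126 are two distinct scores. The fatigability items carry 36/126 = 28.6% of the range of the total and none of the range of the weakness domain.

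**Which score each place names.**

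| Place | Score named |
|---|---|
| SAP 8.3.2, sentence assigning the score to efficacy analysis | Total |
| SAP 8.3.2, sentence introducing the MMRM | Whole scale |
| Protocol 14.3.2, variables for MMRM | Whole scale |
| SAP 8.3.2, null hypothesis | Muscle weakness score |
| SAP 8.3.2, alternative hypothesis | Muscle weakness score |
| SAP 8.3.2, MMRM response | Muscle weakness score |
| SAP 8.3.2, baseline covariate | Muscle weakness score |
| SAP 8.3.2, PEOT rule | Muscle weakness score |
| Protocol 9.3.1, meaning of that term | 0-90 domain |

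Three places point to the total and five operative places use the domain's name. The SAP nowhere defines the muscle weakness score as shorthand for the total. SAP 4.1 does not settle the covariate, because it lists QMG, MG-Composite, MGADL and MGII and not this scale.

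**Comparison with the next section.** SAP 8.3.3 sends the overall fatigue score to efficacy analysis and then tests the fatigue instrument score. No domain of that instrument bears that name, so its response variable is clear. In 8.3.2 the name used for the tested response already belongs to a domain.

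No power calculation is given. The documents contain no SD, between-domain correlation or expected effect for either domain, so any such figure would rest wholly on assumption.

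**The case against.** The strongest reply is that the intended score can be recovered from the text.

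- SAP 8.3.2 plans change from baseline, which is the model response, for the total only.
- Both the sentence introducing the MMRM and Protocol 14.3.2 name the whole scale.
- SAP section 1 makes the protocol the default unless the SAP specifies otherwise. SAP 3.9, which lists changes to protocol-defined analyses, reports only the MGADL change and no move to a single domain.
- SAP Table 3-1 uses muscle weakness as a loose label for the instrument, beside Fatigue, MGADL and MGII.
- The baseline muscle weakness score also appears as covariate in the fatigue and MGII models (SAP 8.3.3 and 8.3.5). That is a separate matter, but it suggests template text rather than a deliberate choice of domain.

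All of this stands as evidence of intent. It does not remove the need for correction, because the shorthand coincides with a term the protocol defines for a different score and it recurs in five operative places.

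A reader might infer that the two scores are equally open and that the sponsor could choose between them after unblinding. The documents do not support that. They favour the total, and listing domain totals is ordinary reporting that creates no second endpoint.

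The stakes are also low. The instrument is newly developed, and SAP 8.3.9 foresees later Rasch work to reduce its items and develop a scoring algorithm. The futility look in SAP 4.4 uses QMG, MG-Composite and MGADL, not this scale.

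**Conclusion.** The point holds as an internal contradiction in SAP 8.3.2. Read literally, the hypotheses and model test the 0-90 domain, contrary to the section's own designating sentence and to Protocol 14.3.2, and omit nine items worth 36 of 126 points. The total is the likelier intent. This rests on the protocol's definition of the term and on the absence of any SAP statement equating it with the total.

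The scope is one 'other' efficacy variable. A reader might infer a threat to the trial's main result, but the primary variable (QMG) and the secondary variables (MG-Composite and MGADL) are specified separately and are unaffected. Nor do the documents support a stated gain or loss of power from using one score rather than the other.

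**What to change.** In SAP 8.3.2, replace *muscle weakness score* with *total muscle weakness severity and fatigability score (0-126)* in the null hypothesis, the alternative hypothesis, the MMRM response, the baseline covariate and the PEOT sentence. This brings the section into line with its own designating sentence and with Protocol 14.3.2.

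The cost is SAP wording only. No data collection changes, and change from baseline in the total is already planned. Descriptive summaries of the two domain scores by arm and visit would be optional. The protocol does not ask for them, and the domain totals are already listed.

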8.3.3 Fatigue Instrument

The fatigue instrument consists of 55 items across 3 domains: 16 physical domain items (with a scale of 16 to 80), 18 mental domain items (with a scale of 18 to 90), and 21 fatigability domain items (with a scale of 21 to 105). The subject will be asked to score each item based on how frequently she/he experienced the item during the past 7 days using a 5-point Likert scale (“none of the time” to “all of the time”). The items of the fatigue instrument will be displayed in a glossary. The overall score ranges from 55 to 275, with a higher result indicating more severe fatigue. All individual item results will be listed per time point including overall score. Change from baseline will be calculated for the overall score and both overall score and change from baseline will be used in descriptive summaries and for efficacy analysis. Overall score will be descriptively summarized by treatment and time point.

Fatigue scale at each assessed post-Randomization Visit (during Dosing Period 1 including Visit 9) will also be analyzed utilizing the MMRM approach. A 1-sided hypothesis test will be performed to test the hypothesis of superiority of UCB7665 7mg/kg vs placebo at Visit 9. The null hypothesis is that the mean change from Baseline in fatigue instrument score is larger or equal in the UCB7665 7mg/kg group than the placebo group. The alternative hypothesis is that the mean change from Baseline in fatigue instrument score is smaller in the UCB7665 7mg/kg group than the placebo group.

The change from baseline of the fatigue instrument score will be analyzed for the FAS using a MMRM ANCOVA that includes terms for week (as categorical effect), treatment group, the Baseline muscle weakness score, and the interaction between treatment group and week. The model will define subject as a random effect and utilize an unstructured covariance pattern. Least Squares (LS) Means for changes from Baseline at Visit 9 (Day 29) for each treatment group will be presented together with LS mean differences (UCB7665 - 7mg/kg vs placebo), p-value and 1 sided 95% CI.

For subjects who prematurely withdraw for any reason before Visit 9 (Day 29), data collected during the PEOT Visit will be used to impute fatigue instrument scores at the next consecutive visit.

8.3.4 MGFA Clinical Classification

The MGFA Clinical Classification is a 5 stage classification (I to V), with a higher class indicating more severe disease. Results of MGFA Clinical Classification will be listed.

The percentage of subjects with each MGFA classification at each scheduled assessment during Treatment and Observation Periods will be calculated and descriptively summarized for the FAS.

8.3.5 MG Impairment Index

The MGII consists of a 22 items patient questionnaire and an 8 item examination. It is divided in two sub-scores reflecting an ocular and a generalized domain. The ocular score is calculated by summing 8 items reflecting ocular impairments. These items are: patient questionnaire items 1 to

6 and examination items 1 and 2. The generalized score is calculated by adding items 7 to 22 from the patient questionnaire and items 3 to 6 from the examination. The complete list of items is given in Table 14–6. The items of MGII will be displayed in a glossary. All individual item results will be listed per time point including overall score. Change from baseline will be calculated for the overall score and sub-scores (ocular and generalized domain). The overall score, two sub-scores and their change from baseline will be used in descriptive summaries and for efficacy analysis. For overall score and sub-scores, missing items will be imputed according to the rules set in Section 14.5. Descriptive summaries will be by treatment and time point.

The change from baseline MGII scale at each assessed post-Randomization Visit (during Dosing Period 1 including Visit 9) will also be analyzed utilizing the MMRM approach. A 1-sided hypothesis test will be performed to test the hypothesis of superiority of UCB7665 7mg/kg vs placebo at Visit 9. The null hypothesis is that the mean change from Baseline in MGII score is larger or equal in the UCB7665 7mg/kg group than the placebo group. The alternative hypothesis is that the mean change from Baseline in MGII score is smaller in the UCB7665 7mg/kg group than the placebo group.

The change from baseline of the MGII score will be analyzed for the FAS using a MMRM ANCOVA that includes terms for week (as categorical effect), treatment group, the Baseline muscle weakness score, and the interaction between treatment group and week. The model will define subject as a random effect and utilize an unstructured covariance pattern. Least Squares (LS) Means for changes from Baseline at Visit 9 (Day 29) for each treatment group will be presented together with LS mean differences (UCB7665 - 7mg/kg vs placebo), p-value and 1 sided 95% CI.

For subjects who prematurely withdraw for any reason before Visit 9 (Day 29), data collected during the PEOT Visit will be used to impute MGII scores at the next consecutive visit.

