Unless stated otherwise, all statistical tests will be 1-sided and conducted at 0.05 alpha levels (due to the character of the study no alpha adjustment for multiplicity will be done). For Dosing Period 2, only descriptive analyses will be performed.

Data listings containing all documented data and all calculated data will be generated.

Baseline will be the last non-missing data collected prior to the first dose of IMP in Dosing Period 1, and measurement-specific Baseline values will be defined in the SAP.

Planned efficacy analyses 14.3

For all efficacy analyses the Treatment Groups used for analysis during Dosing Period 1 and during Dosing Period 2/Observation Period will be as defined in Section 14.2. Efficacy endpoints will be analyzed using descriptive statistics for data obtained during Treatment Period 2 and Observation Period. Further details will be provided in SAP.

ر 14.3.1 Analysis of the primary efficacy variable

The primary efficacy variable is the change from Baseline in QMG score to Visit 9 (Day 29), prior to the first infusion of IMP in Dosing Period 2.

A 1-sided hypothesis test will be performed to test the primary hypothesis of superiority of UCB7665 7mg/kg vs placebo at Visit 9. The null hypothesis is that there is no difference in the change from Baseline between Treatment Groups. The alternative hypothesis is that the mean change from Baseline in QMG score is smaller in the UCB7665 7mg/kg group than the placebo group.

The primary analysis of the primary variable will be based on a mixed model repeated measures (MMRM) analysis of covariance (ANCOVA) that includes terms for treatment group, week, the Baseline QMG score, and the interaction between treatment group and week. The model will define patient as a random effect and utilize an unstructured covariance pattern.

Least Squares (LS) Means for changes from Baseline at Visit 9 for each treatment group will be presented together with LS mean differences (UCB7665 - 7mg/kg vs placebo) and 1-sided 95% confidence interval (CI).

For subjects who prematurely withdraw for any reason before Visit 9 (Day 29), data collected during the PEOT Visit will be used to impute QMG scores at the next consecutive visit.

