1 INTRODUCTION

The purpose of this statistical analysis plan (SAP) is to provide all information that is necessary to perform the required statistical analysis of MG0002. It also defines the summary tables, figures and listings (TFLs) to be included in the final Clinical Study Report (CSR) according to the protocol.

This SAP is based upon, and assumes familiarity, with the following study documents:

1. Final Protocol: 21 Oct 2016
2. Protocol Amendment 1: 07 Feb 2017
3. Protocol Amendment 2: 15 Sep 2017

Unless specified below, the study will be analyzed as described in the most recent version of the protocol/amendment (European Union Drug Regulating Authorities Clinical Trials [EudraCT]-Number: 2016-002698-36).

If a future protocol amendment necessitates a substantial change to the statistical analysis of the study data, this SAP will be amended accordingly. If, after database lock, additional analyses are required to supplement the planned analyses described in this SAP, those unplanned analyses will not be described in an amended SAP but they will be described in a separate statistical analysis plan. However, if analysis definitions have to be modified or updated, a SAP amendment will be required. The content of this SAP is compatible with the International Council for Harmonisation (ICH)/ Food and Drug Administration (FDA) E9 Guidance documents. UCB is the sponsor and PAREXEL International is the Contract Research Organization (CRO) for this study.

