4 STATISTICAL/ANALYTICAL ISSUES

4.1 Adjustments for covariates

In the analysis of the efficacy variables, the Baseline value of the QMG, MG-composite score, MGADL score or MGII score will be used as a covariate in the analysis of the respective variable.

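### SAP 8.3.5 (MGII) and 8.3.3 (fatigue) adjust for Baseline muscle weakness instead of the scale's own Baseline; for MGII this contradicts SAP 4.1

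*SAP*

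**What the plan says.** - **MGII, SAP 8.3.5.** The change in "MGII score will be analyzed for the FAS using a MMRM ANCOVA that includes terms for week (as categorical effect), treatment group, the Baseline muscle" (in full, the Baseline muscle weakness score), plus the treatment-by-week interaction.
- **Fatigue, SAP 8.3.3.** The change in this "instrument score will be analyzed for the FAS using a MMRM ANCOVA that includes terms for week (as categorical effect), treatment group, the Baseline muscle" (in full, the Baseline muscle weakness score), plus the same interaction.
- **Muscle weakness, SAP 8.3.2.** "The change from baseline of the muscle weakness score will be analyzed for the FAS using a MMRM ANCOVA that includes terms for week", treatment group and the Baseline muscle weakness score. Here the covariate is the outcome's own Baseline.
- **General rule, SAP 4.1.** The Baseline value of the QMG, MG-Composite, "MGADL score or MGII score will be used as a covariate in the analysis of the respective variable". The fatigue and muscle weakness scales are not listed.
- **Protocol 14.3.2.** The secondary variables and the other scales, MGII and fatigue among them, "will also be analyzed utilizing the MMRM approach similarly to the change from Baseline in QMG for the FAS".
- **Protocol 14.3.1.** The QMG model "includes terms for treatment group, week, the Baseline QMG score, and the interaction between treatment group and week".
- **SAP 1.** "Unless specified below, the study will be analyzed as described in the most recent version of the protocol/amendment". SAP 3.9, which lists changes to the protocol-defined analyses, mentions only MGADL.

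**The concern.** For MGII, the programmer has two SAP instructions that name different covariates, and the SAP does not say which takes precedence. For fatigue, 8.3.3 is the only SAP instruction, so it would be run as written although it is probably unintended.

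Both analyses are planned 1-sided superiority tests at Visit 9 with a p-value and a confidence interval, so the model should be settled before unblinding. In a trial with a target of 40 evaluable subjects, a chance difference between arms in the scale's own Baseline is quite possible. Baseline muscle weakness corrects such a difference only in part. Data for planning later studies are a secondary objective, so precision on these scales has some use.

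**Working it through.** **Text comparison**

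| Outcome | SAP section | Baseline covariate | Own Baseline? |
|---|---|---|---|
| QMG | 8.1.2 | QMG | yes |
| MG-Composite | 8.2.1 | MG-Composite | yes |
| MGADL | 8.2.2 | MGADL | yes |
| Muscle weakness | 8.3.2 | muscle weakness | yes |
| Fatigue | 8.3.3 | muscle weakness | **no** |
| MGII | 8.3.5 | muscle weakness | **no** (4.1 says MGII) |

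For MG-Composite, for example, the model sentence names the "Baseline MG-composite score, and the interaction between treatment group and week". The sentences in 8.3.2, 8.3.3 and 8.3.5 are the same apart from the outcome name. SAP Table 3-1 lists a predose Day 1 Baseline for both MGII and fatigue, so data availability does not explain the switch.

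**Size**

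There is no plan figure to reproduce, and the documents give no correlations for these scales. The inputs below are therefore assumptions, apart from n:

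- rho, the correlation of the scale's own Baseline with its Visit 9 value: 0.5 to 0.8.
- q, the correlation of Baseline muscle weakness with the scale's own Baseline: 0.3 to 0.9.
- Equal unit variances, with muscle weakness related to the Visit 9 score only through the own Baseline.
- n = 20 per arm, from the target of 40 evaluable subjects and 1:1 randomization.

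Formulas for the change score:

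- Variance given own Baseline: 1 − rho².
- Variance given muscle weakness: 2(1 − rho) − q²(1 − rho)².
- Variance ratio: [2 − q²(1 − rho)]/(1 + rho). The SE ratio is its square root.
- SE with own Baseline: √[(1 − rho²)·2/n].
- SD of the Baseline-imbalance error left uncorrected: √(2/n)·(1 − rho)·√(1 − q²).
- Mean error carried when the arm difference in own Baseline is one SD of its chance distribution, √(2/20) = 0.316: √(2/n)·(1 − rho)·(1 − q²).

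Example at q = 0.3, rho = 0.5: 2(0.5) − 0.09·0.25 = 0.9775 against 1 − 0.25 = 0.75. The variance ratio is 0.9775/0.75 = 1.303 and the SE ratio 1.142.

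| q, rho | Variance ratio | SE ratio | Own-Baseline SE | Uncorrected-error SD | Mean carried error |
|---|---|---|---|---|---|
| 0.3, 0.5 | 1.303 | 1.142 | 0.274 | 0.151 | 0.144 |
| 0.5, 0.6 | 1.187 | 1.090 | 0.253 | 0.110 | 0.095 |
| 0.7, 0.6 | 1.127 | 1.062 | 0.253 | 0.090 | 0.065 |
| 0.7, 0.7 | 1.090 | 1.044 | 0.226 | 0.068 | 0.048 |
| 0.9, 0.8 | 1.021 | 1.011 | 0.190 | 0.028 | 0.012 |

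The last three columns are in SDs of the score.

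**Simulation of the repeated-measures model.** The settings were 40 subjects 1:1, complete data, no treatment effect, unstructured covariance and 1,500 runs per row. The SE ratio was 1.01 to 1.14 for both scales. The 1-sided type I error with the written covariate was 0.040 to 0.063 (Monte Carlo SE 0.006), against 0.039 to 0.061 with own Baseline.

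**Sensitivity.** Let the correlation of Baseline muscle weakness with the Visit 9 score be q·rho + d. The variance given muscle weakness becomes 2(1 − rho) − (q·rho + d − q)². Over the five rows the SE ratio is:

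| d | SE ratio |
|---|---|
| −0.10 | 0.945 to 1.118 |
| −0.05 | 0.982 to 1.131 |
| +0.05 | 1.032 to 1.149 |
| +0.10 | 1.046 to 1.153 |

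**The case against.** - **Low tier.** Both scales are other efficacy variables in a Phase 2a trial without multiplicity control. QMG, MG-Composite and MGADL use their own Baselines, and the futility look uses only those three. This stands, and it limits the severity.
- **The protocol limb is weaker.** Protocol 14.3.2 asks for a similar analysis, not an identical one, and SAP 1 lets the SAP override the protocol. For fatigue there is thus one explicit covariate and no contradiction within the SAP. This stands as far as it goes: the departure is by implication, and a copying error is inferred, not proven. SAP 1 does not resolve the MGII conflict, because both rules are in the SAP.
- **Both covariates could be meant for MGII.** Read cumulatively, 4.1 and 8.3.5 would put MGII and muscle weakness in the same model, and no precision would be lost. This is strained, since every parallel section names a single Baseline. It also confirms that the text is ambiguous.
- **The size is assumed, and its direction is not certain.** This stands. With d = −0.10, the written covariate is the more precise one in two of the five rows (SE ratios 0.994 and 0.945).

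**Conclusion.** The concern holds. For MGII the SAP contradicts itself (8.3.5 against 4.1), whatever the effect on precision. For fatigue the covariate departs by implication, and without declaration, from Protocol 14.3.2. Validity is not at risk: randomization keeps the estimates unbiased on average, and the simulated type I error stayed close to 0.05. The likely cost is modest precision, with an SE 1% to 14% larger under the stated assumptions, and possibly none if muscle weakness predicts the Visit 9 score differently from what was assumed. No primary, secondary or futility result depends on either model. It should be fixed because it is a real conflict in a pre-specified test and the correction is simple.

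**What to change.** - In SAP 8.3.5, name the Baseline MGII score as the covariate. If the ocular or generalized sub-scores are modelled, use the matching sub-score Baseline.
- In SAP 8.3.3, name the Baseline fatigue instrument score.
- In SAP 4.1, add the fatigue and muscle weakness scales to the list.
- If adjustment for muscle weakness is really intended, declare and justify it in SAP 3.9 and correct 4.1 for MGII.

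The cost is a few words and no new data. SAP 1 requires an SAP amendment when analysis definitions are modified, and the current amended SAP carries an approval date of 10 Jul 2018, so a further amendment is needed. It should be in place before anyone involved in the choice sees unblinded results, including the third interim analysis, which reports the primary and secondary variables once all subjects have attended Visit 9.
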